2.8.1 Adverse events

AEs will be coded and graded using the latest version of MedDRA and CTCAE, respectively, available at the time of reporting. If CTCAE grading does not exist for an AE, grades 1, 2, 3, or 4 corresponding to the severity of mild, moderate, severe, and life-threatening, respectively, will be used. CTCAE grade 5 (death) will not be used in this study. Death information will be collected on the 'End of Treatment', 'Survival Information' and 'Death' eCRF pages.

AE Summaries (CSR outputs)

Primary AE summaries will include all AEs occurring during the on-treatment period. Additional select summaries will be produced using all treatment related AEs starting or worsening during the on-treatment or post-treatment period.

All AEs collected in the AE (e)CRF page will be listed along with the information collected on those AEs e.g. AE relationship to study drug, AE outcome etc. AEs starting during the pre- or post-treatment periods will be flagged in the listings.

AEs will be summarized by number and percentage of subjects having at least one AE, having at least one AE in each primary system organ class (SOC) and for each preferred term (PT) using MedDRA coding. A subject with multiple occurrences of an AE will be counted only once in the respective AE category. A subject with multiple CTCAE grades for the same preferred term will be summarized under the maximum CTCAE grade recorded for the event. AE with missing CTCAE grade will be included in the 'All grades' column of the summary tables.

In AE summaries the primary system organ class will be presented alphabetically and the preferred terms will be sorted within primary SOC in descending frequency. The sort order for the preferred term will be based on their frequency in the PDR001 treatment group

The following AE summaries will be produced for AEs starting or worsening during the on-treatment period:

- Overview of adverse events and deaths (number and % of subjects who died, with any AE, any SAE, any dose reductions/interruptions, AE leading to discontinuation)
- AEs by SOC and/or PT, summarized by relationship (all AEs and AEs related to study treatment);

- Seriousness (SAEs, and non-SAEs);
- Leading to treatment discontinuation;
- Leading to dose interruption/adjustment;
- Requiring additional therapy;
- Leading to fatal outcome;

The following AE summaries will be produced for PDR001 for all AEs starting or worsening during the on-treatment or post-treatment periods:

- AEs suspected to be study treatment related;
- SAEs related to study treatment

The following listings will be produced:

- All adverse events (safety set)

Deaths (CSR Outputs)

Separate summaries for on-treatment and all deaths (including post-treatment deaths) will be produced by treatment arm, system organ class and preferred term.

All deaths will be listed for the safety set, deaths occurring after the treatment period will be flagged.

EudraCT and clinicaltrials.gov requirements for AEs and Deaths summaries

For the legal requirements of clinicaltrials.gov and EudraCT, two required tables on treatment-emergent adverse events which are not serious adverse events with an incidence greater than 5% and on treatment emergent SAEs and SAEs suspected to be related to study treatment will be provided by SOC and PT on the safety set population. These summaries will include any events starting or worsening in the on-treatment period.

If for a same patient, several consecutive AEs (irrespective of study treatment causality, seriousness and severity) occurred with the same SOC and PT:

- a single occurrence will be counted if there is ≤ 1 day gap between the end date of the preceding AE and the start date of the consecutive AE
- more than one occurrence will be counted if there is > 1 day gap between the end date of the preceding AE and the start date of the consecutive AE

For occurrence, the presence of at least one SAE / SAE suspected to be related to study treatment / non SAE has to be checked in a block e.g., among AE's in a ≤ 1 day gap block, if at least one SAE is occurring, then one occurrence is calculated for that SAE.

The number of deaths resulting from SAEs suspected to be related to study treatment and SAEs irrespective of study treatment relationship will be provided by PT.

Adverse events of special interests / grouping of AEs

An adverse event of special interest is a grouping of adverse events that are of scientific and medical concern specific to compound PDR001. These groupings are defined using MedDRA terms, SMQs (standardized MedDRA queries), HGLTs (high level group terms), HLT (high

[figure not shown]
level terms) and PTs (preferred terms). Customized SMQs (Novartis MedDRA queries, NMQ) may also be used. A NMQ is a customized group of search terms which defines a medical concept for which there is no official SMQ available or the available SMQ does not completely fit the need. It may include a combination of single terms and/or an existing SMQ, narrow or broad.

For each specified AESI, number and percentage of subjects with at least one event of the AESI occurring during on-treatment period will be summarized.

Summaries of these AESIs will be provided for treatment group PDR001 and Crossover. A listing of all grouping levels down to the MedDRA preferred terms used to define each AESI will be generated.

Summarize adverse events in Crossover treatment group

Patients from randomized to Chemotherapy treatment group are allowed to crossover to PDR001 group after confirmation of PD to chemotherapy. Below diagram specifies how to summarize the AEs for crossover treatment group.

For Scenario 1: do not count AE X (Grade 2) in Period 2 (PDR treatment), as it is an AE starts in Period 1 (Chemotherapy) and resolving during Period 2;

For Scenario 2: count AE X (Grade 2) in Period 2, as this AE starts at least 1 day after previous AE, indicates it is a new AE starts in period 2, not a resolving previous AE;

For Scenario 3: count AE X (Grade 3) in Period 2, as it is a worsening AE

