### 7.1.3 Discontinuation of study treatment

Patients may voluntarily discontinue from the study treatment for any reason at any time. If a patient decides to discontinue from the study treatment, the investigator should make a reasonable effort (e.g. telephone, e-mail, letter) to determine the primary reason for this decision and record this information in the patient's chart and on the appropriate eCRF. They may be considered discontinued if they state an intention to withdraw or fail to return for visits.

The investigator should discontinue study treatment for a given patient if, on balance, he/she believes that continuation would be detrimental to the patient's well-being.

Study treatment may be discontinued under the following circumstances:

- Adverse event
- Lost to follow-up
- Physician's decision
- Progressive disease as per irRC (not as per RECIST v1.1; patients treated with PDR001)
- Progressive disease as per RECIST v1.1 (patients treated with chemotherapy)
- Confirmed Complete response as per RECIST v1.1 (patients treated with PDR001)
- Study terminated by Novartis
- Patient/guardian decision
- Protocol deviation
- Technical problems

Study treatment must be discontinued if any of the following occur:

- Death
- Pregnancy

Patients who discontinue study treatment should undergo as soon as possible and within 14 days of the last dose of study drug or within 14 days of the decision to discontinue study treatment, an End of Treatment (EoT1) visit and then be discontinued from the study treatment (please refer to [Table 7-1](#) and [Table 7-3](#) for list of assessments to be performed).

Patients in the control arm, who switch to PDR001 treatment, should have an EoT visit (EoT2) once they are discontinued from PDR001 treatment (please refer to [Table 7-3](#) for list of assessments to be performed).

If the decision to discontinue the patient occurs at a regular scheduled visit, that visit may become the EoT visit rather than having the patient return for an additional visit. An End of Treatment Phase Disposition eCRF should be completed, giving the reason for stopping the study treatment. End of treatment/Premature withdrawal visit is not considered as the end of the study. The investigator must also contact IRT to register the patient's discontinuation from study treatment.

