## **7.2 Assessment types**

### **7.2.1 Efficacy assessments**

Tumor response will be assessed locally and centrally according to the two following criteria

1. RECIST v1.1 ([Appendix 1](#), [Eisenhauer et al 2009](#)).
2. irRC ([Appendix 2](#), based on [Wolchok et al 2009](#) and [Nishino et al 2013](#)).

Imaging data will be centrally collected in blinded fashion and checked for quality by an imaging Contract Research Organization (CRO) designated by Novartis. The results of the central evaluations will be used for primary analysis purposes. The local investigator's assessment will be used for treatment decision making (study discontinuation due to PD as per irRC for patients treated with PDR001). Patients in PDR001 treatment will not be discontinued from the study treatment due to progressive disease as per RECIST v1.1. Similar to RECIST v1.1, irCR and irPR must be confirmed at a new assessment after at least 4 weeks. In addition, unlike RECIST v1.1, irPD also requires confirmation at a new assessment after at least 4 weeks. Please refer to [Appendix 1](#) and [Appendix 2](#) for further details.

Patients in the control arm who progressed after chemotherapy are allowed to crossover to the PDR001 after their documented progression is confirmed as per RECIST v1.1 based on the independent central review.

The independent central review of imaging data will be terminated for the whole study when both criteria are met, 1) decisions are made based on central review results for all chemotherapy arm patients on whether to crossover; 2) all patients have reached a minimum of 12 months follow up after the first dose of study treatment (unless have been lost to follow-up).

The imaging assessment collection plan is presented in [Table 7-4](#). Details of the central review process will be described in the independent review charter.

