#### **10.5.3.2 Adverse events (AEs)**

Summary tables for adverse events (AEs) have to include only AEs that started or worsened during the on-treatment period, the **treatment-emergent** AEs. However, all safety data (including those from the pre and post-treatment periods) will be listed and those collected during the pre-treatment and post-treatment period are to be flagged.

The incidence of treatment-emergent adverse events (new or worsening from screening/baseline) will be summarized by system organ class and or preferred term, severity (based on CTCAE grades), type of adverse event, relation to study treatment by treatment group.

Deaths reportable as SAEs, and non-fatal serious adverse events will be listed by patient and tabulated by type of adverse event and treatment group.

The following summaries will be produced for the combined on-treatment and post-treatment periods: AEs related to the study treatment by preferred term; SAEs related to the study treatment by preferred term; AEs of special interest related to the study treatment.

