### **10.8 Sample size calculation**

Assuming a 2:1 randomization ratio of PDR001 vs. Comparator, 70 events (PD or death) are to be observed in the randomized Phase II to provide 85% power to detect a 0.55 hazard ratio in terms of PFS (corresponding to a median PFS of 10 months in PDR001 group and 5.5 months in the Comparator group), using a log-rank test at a 1-sided significance level of 0.1.

The final primary analysis of PFS will be done using a Bayesian proportional hazard model when there are at least 70 events observed. Based on the simulation results under different scenarios (see [Appendix 3](#)), 70 events provide reasonable operating characteristics in terms of the probability of obtaining a positive result (as defined in [Section 10.4.2](#)). Using the Bayesian

Cox PH model with mixture MAP prior for the yields reasonable 1-sided type I error (0.081) assuming no efficacy (HR=1) and power (0.92) assuming substantial efficacy (HR=0.55) when current data is in alignment with historical data.

Considering a uniform recruitment time of about 14 months and a 15% drop out rate at 12 months, approximately 114 patients need to be randomized in a 2:1 ratio to the two arms in order to observe 70 events after approximately 6 months follow up (approximately 20 months after FPFV):

- 76 patients to the PDR001 arm
- 38 patients to the control arm

EAST® trial design software v5.4 is used to compute the sample size.

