For PDR001 arm, an on-treatment assessment/event is defined as any assessment/event obtained in the time interval from the start date of study treatment until the minimum date of (last date of study treatment + 30 days).

For crossover treatment group, an on-treatment assessment/event is defined as any assessment/event obtained in the time interval from the start date of PDR001 treatment until the minimum date of (last date of study treatment + 30 days).

For chemotherapy arm, an on-treatment assessment/event is defined as any assessment/event obtained in the time interval from the start date of study treatment until the minimum date of (the last date of study treatment + 30 days inclusive, start of crossover PDR treatment if crossed over).

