2.8 Safety analysis

Summaries and listings described in this section will be done by study treatment groups based on the Safety set:

- PDR001
- Chemotherapy
- Crossover

For crossover treatment group, summaries will be done if there are more than 10 crossover patients.

The assessment of safety is based on the type and frequency of Adverse Events (AEs) as well as on the number of laboratory values that fall outside of pre-determined ranges (Common Toxicity Criteria for Adverse Events (CTCAE) grading limits or normal ranges as appropriate). Other safety data include electrocardiogram and vital signs.

The overall observation period will be divided into three mutually exclusive segments:

- Pre-treatment period: from day of patient's informed consent to the day before first dose of study treatment,
- On-treatment period: from day of first dose of study treatment to the end of safety follow up, i.e., for PDR001, to 30 days after last dose of PDR001; For chemotherapy, to 30 days after last dose of chemotherapy.

- Post-treatment period: starting at Day 31 after last dose of PDR001 for PDR001 treatment group; Starting at Day 31 after last dose of chemotherapy for chemotherapy treatment group.

If dates are incomplete in a way that clear assignment to pre-, on-, post-treatment period cannot be made, then the respective data will be assigned to the on-treatment period.

Safety summaries will primarily be based on all data from the on-treatment period. Following last administration of PDR001, adverse events (including serious adverse events), and new antineoplastic therapies are collected for a period of 150 days. Following start of new antineoplastic therapy only treatment related adverse events will be collected. Select summaries of related adverse events will be produced for the combined on-treatment and post-treatment periods ([Section 2.8.1](#)).

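### No adverse-event summary allows for time at risk: crude percentages are shown by treatment group over a window whose length follows treatment duration

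*SAP*

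**What the plan says.** **Measure.** SAP 2.8.1 says "AEs will be summarized by number and percentage of subjects having at least one AE", overall and by system organ class and preferred term, and adds "A subject with multiple occurrences of an AE will be counted only once in the respective AE category". Protocol 10.5.3.2 plans the same kind of table: "The incidence of treatment-emergent adverse events (new or worsening from screening/baseline) will be summarized by system organ class" and further breakdowns, by treatment group.

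**Window.** SAP 2.8 defines "On-treatment period: from day of first dose of study treatment to the end of safety follow up, i.e., for PDR001, to 30 days" after the last dose, with the same 30 days for chemotherapy. Protocol 10.5.3.1 agrees. For the chemotherapy arm, SAP 2.1.1 ends the window at the earlier of last dose plus 30 days and "start of crossover PDR treatment if crossed over".

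**Treatment duration.** Protocol 7.2.1 states "Patients in PDR001 treatment will not be discontinued from the study treatment due to progressive disease as per RECIST v1.1". Protocol Appendix 2 requires immune-related progression to be confirmed at least 4 weeks later. Protocol 7.1.3 lists RECIST progression among the circumstances in which chemotherapy may be stopped.

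**Exposure.** SAP 2.5.1 summarises duration of exposure for PDR001 and for chemotherapy. Neither document links exposure to AE counts through a rate per patient-time, a time-to-first-event estimate or a common fixed window. The registry tables in SAP 2.8.1 also count repeat occurrences, again without person-time.

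**The concern.** The percentage of patients with at least one event rises with the length of observation. If one group is treated for longer, its percentage is higher at the same underlying event rate, and the table cannot show how much of a difference is toxicity and how much is time.

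This matters because Protocol 4.1 and SAP 1.1 describe the study as evaluating the safety, as well as the efficacy, of PDR001 versus the investigator's choice of treatment. The groups will be read against each other even though no AE test is planned. Were PDR001 to delay progression, its own benefit would raise its AE percentages. Were it stopped sooner than chemotherapy, the same tables would flatter it.

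**Working it through.** **1. The plan's own figure.** The only stated numbers bearing on expected duration are in Protocol 10.8 and SAP 3: 70 events, 85% power, hazard ratio 0.55, one-sided 0.10, 2:1 allocation, "corresponding to a median PFS of 10 months in PDR001 group and 5.5 months in the Comparator group". Schoenfeld's formula gives (1.2816 + 1.0364)² / [(2/9) × (ln 0.55)²] = 67.65, so 68 events. Power with 70 events is 0.859. The stated figures reproduce, and 5.5/10 = 0.55.

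**2. Illustration under the design medians.** These assumptions are not in the documents:
- treatment duration is exponential with the design PFS median m, so μ = ln 2 / m;
- the tail is 30 days = 0.986 months, with no cut at crossover;
- both groups have the same constant first-AE rate L, taken as 0.02 to 0.05 per month;
- no treatment beyond progression is added.

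Mean window = m/ln 2 + 0.986: 15.4 months for PDR001 and 8.9 for chemotherapy.

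Crude percentage = 1 − e^(−0.986 L) × μ/(μ + L), with μ = 0.0693 (PDR001) and 0.1260 (chemotherapy):

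| L per month | PDR001 | Chemotherapy | Ratio |
|---|---|---|---|
| 0.02 | 1 − 0.9805 × 0.7761 = 23.9% | 1 − 0.9805 × 0.8630 = 15.4% | 1.55 |
| 0.05 | 1 − 0.9519 × 0.5809 = 44.7% | 1 − 0.9519 × 0.7160 = 31.8% | 1.40 |

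For very common events the ratio shrinks: at L = 0.50 it is 92.6% versus 87.7% (1.06).

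**3. Sensitivity to duration.** If treatment lasts half as long in both groups (medians 5 and 2.75 months), the figures are about 14% versus 9% and 30% versus 21%. If the PDR001 median is 4.0 months (μ = 0.1733) and chemotherapy stays at 5.5, L = 0.05 gives 1 − 0.9519 × 0.7761 = 26.1% versus 31.8%. The direction has reversed.

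**4. Treatment past RECIST progression, with equal PFS.** The window runs from the last dose, and PDR001 is given every 4 weeks (Protocol Table 6-1). Assume doses fall on scan days and the patient stays on until confirmation.
- Confirmation 4 weeks later: the last dose is on the day of first progression, so the window ends at progression + 30 days. Daily chemotherapy stopped at progression ends at the same point, so there is no excess.
- Confirmation 8 weeks later: one further dose, so 28 days = 0.92 months more. Against a mean window of 8.92 months this is 10%. At 5.5 months PFS in both groups, the crude percentages are 16.9% versus 15.4% (L = 0.02) and 34.9% versus 31.8% (L = 0.05). Mean windows would then be equal at a PDR001 median of 5.5 − 0.92 × ln 2 = 4.9 months.

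Cyclic chemotherapy, or a window cut at crossover, would widen the gap somewhat.

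**5. What the documents show of actual duration.** The study-status paragraphs give 122 randomised, 82 to PDR001 and so 40 to chemotherapy. On 10 August 2018, 18/82 (22.0%) were on PDR001 as randomised and 5/40 (12.5%) on chemotherapy (Fisher p = 0.32). On 21 May 2019 the counts were 11/82 (13.4%) and 0/40 (p = 0.016). This suggests a longer tail of PDR001 treatment. It does not give mean exposure.

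**6. Does a rate remove the effect?** With constant L, expected time at risk to first event is the crude proportion divided by L. At L = 0.05 this is 0.447/0.05 = 8.94 months and 0.318/0.05 = 6.4 months per patient. Dividing events by time returns 0.05 per month, or 60 per 100 patient-years, in both groups.

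**The case against.** The best case for the plan is that its safety objective is to characterise PDR001. No AE test or decision rule compares the groups, and crude incidence with exposure reported elsewhere is a legitimate description for a phase II trial. The main window is 30 days in both groups although PDR001 events are collected for 150 days. Deaths are tabulated on-treatment and overall, so fatal outcomes are not confined to the treatment-length window. The table shells, and the interim report with its analysis plan, were not available and may hold more. All of this stands. It limits the consequence, but it does not give the reader of the side-by-side tables a way to separate rate from time.

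Four stronger readings are tempting, and the documents do not support them:
- *PDR001 will necessarily look more harmful at an equal rate.* That needs longer PDR001 exposure, and neither document gives exposure times.
- *The gap is the one implied by 10 versus 5.5 months.* Those are planning values. SAP 2.2.3 records that the primary efficacy analysis was not statistically significant.
- *Waiting for confirmation always lengthens the PDR001 window by 4 to 8 weeks.* Because the window starts from the last 4-weekly dose, a 4-week confirmation may add nothing. Continuation also depends on clinical status (Protocol 7.1.2).
- *Chemotherapy must stop at RECIST progression.* Protocol 7.1.3 says only that treatment may be discontinued, and 7.2.1 prefers continuation while central review is awaited.

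**Conclusion.** The point holds as a weakness of presentation. Every AE percentage is taken over a window set by treatment duration, the rules make that duration potentially unequal, and no planned AE output accounts for it.

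The illustrative excess on PDR001 is about 8.5 to 13 percentage points (24% versus 15% up to 45% versus 32%). It rests on exponential durations at the design medians and an equal constant rate of 0.02 to 0.05 per month. At equal PFS, the post-progression rule adds between nothing and about 1.5 to 3 points at those rates. The actual size cannot be derived from the documents, and the sign depends on which group was exposed for longer. Interpretation of a secondary objective is affected; the validity of the trial is not.

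**What to change.** In SAP 2.8.1 keep the crude tables. For any AE, related AE, SAE, Grade 3/4 AE and AE leading to discontinuation, add by treatment group, as supportive tables shown beside duration of exposure:

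- (a) patients with a first event per 100 patient-years at risk;
- (b) cumulative incidence of first event at a common early time such as 24 weeks, with death as a competing event. For AEs leading to discontinuation, discontinuation for other reasons should also be a competing event.

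State that differences between PDR001 and chemotherapy are to be read from the crude tables together with (a) and (b). Neither addition should stand alone. The rate assumes a constant hazard, so if events cluster early, long follow-up dilutes it. A plain Kaplan-Meier estimate is not a substitute for (b), because it treats death and stopping as uninformative censoring, which is untenable for events that themselves end treatment.

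The cost is a paragraph of SAP text and one or two tables from dosing and AE dates already collected.

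### SAP 2.8.1 leaves out, without declaring it, the protocol's summary of treatment-related AESIs over the on- and post-treatment periods taken together

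*SAP*

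**What the plan says.** **Protocol.** Section 10.5.3.2 introduces its combined-period list with "The following summaries will be produced for the combined on-treatment and post-treatment periods: AEs related to the study treatment by preferred term". It then adds related SAEs by preferred term and, as the third item, "AEs of special interest related to the study treatment". Section 10.5.3.1 bases safety summaries primarily on the on-treatment period, which ends 30 days after the last dose, and treats the combined-period tables as a selected supplement.

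**SAP.** Section 2.8.1 has a matching list, introduced by "The following AE summaries will be produced for PDR001 for all AEs starting or worsening during the on-treatment or post-treatment periods". It has two items: "AEs suspected to be study treatment related" and "SAEs related to study treatment". The text then moves on to listings. AESIs come later in the same section, under their own sub-heading, where the "number and percentage of subjects with at least one event of the AESI occurring during on-treatment period will be summarized", for the PDR001 and crossover groups. The same passage also provides a listing of the MedDRA terms that define each AESI.

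**Windows.** SAP 2.8 ends the on-treatment period, "for PDR001, to 30 days after last dose of PDR001". The next paragraph but one states: "Following last administration of PDR001, adverse events (including serious adverse events), and new antineoplastic therapies are collected for a period of 150 days".

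**Declared changes.** SAP section 4 has one entry, 4.1, on COVID-19.

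**The concern.** An AESI is a grouping of MedDRA terms chosen because it matters for this compound (SAP 2.8.1). The protocol's third combined-period summary is the one place where late, treatment-related AESIs would be counted per patient and per grouping. If the SAP is followed as written, that count is not produced, and a reader of the final CSR gets grouped AESI figures that stop at day 30 after the last dose.

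The change is also unexplained. Elsewhere this SAP says when it drops content from the final CSR: the per-protocol sensitivity analysis (2.2), subgroups (2.2.3), medical history, prior therapy and disease history (2.3.3 to 2.3.5), and concomitant therapies (2.5.2). Related AESIs over the combined period have no such statement, so a reader cannot tell a decision from an oversight.

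**Working it through.** The plan gives no sample size, power or alpha figure on this point. The check compares the two lists and then does simple arithmetic on the windows.

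**Step 1. The two lists side by side**

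| Summary over on- and post-treatment periods | Protocol 10.5.3.2 | SAP 2.8.1 (PDR001) |
|---|---|---|
| Related AEs | yes | yes |
| Related SAEs | yes | yes |
| Related AESIs | yes | absent |

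The protocol lists three and the SAP two. The difference is exactly the AESI item.

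**Step 2. Does the SAP's AESI table fill the gap?** No. It stops at the end of the on-treatment period. As worded, it also counts patients with any event in the grouping and does not separate related events.

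**Step 3. Post-dose window**

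- Collection after the last PDR001 dose: 150 days (protocol 7.1.5 and 10.5.3.1; SAP 2.8).
- End of the on-treatment period: 30 days after the last dose (protocol 10.5.3.1; SAP 2.8).
- Days with no grouped AESI count: 150 − 30 = 120 (days 31 to 150).
- Share of post-dose follow-up: 120 / 150 = 0.80, or 80%. Covered: 30 / 150 = 20%.
- With the third summary restored: 150 / 150 = 100%.

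**Step 4. Can the count be rebuilt from the retained summaries?** Not by adding preferred-term counts. A patient with two different terms in one AESI grouping counts once for the grouping but twice in the sum of the term counts. The grouped count lies somewhere between the largest single term count and the sum, and the summary tables do not say where. Recovering it means going patient by patient through the AE listing with the AESI term listing in hand.

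**Step 5. Is the change recorded?** SAP section 4 contains only the COVID-19 entry, so it is not.

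**The case against.** The strongest reply is that this is one supplementary table in a deliberately shortened final-CSR plan, and that nothing is hidden. Much of that stands:

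- **The events are still reported.** Related AEs and related SAEs on days 31-150 appear in the two retained combined-period summaries for PDR001. All AEs are listed, with post-treatment ones flagged, and the AESI term listing allows late AESIs to be identified. What is missing is the grouped per-patient count.
- **The on-treatment AESI table is not a departure.** A reader might infer from its 30-day limit that the table itself breaks the protocol. It does not, because both documents make the on-treatment period primary. The protocol also never promised an all-causality AESI table to day 150; its third item covers related events only.
- **Crossover patients.** A reader might infer that the protocol requires the table for them too. Section 10.5.3.2 does not mention crossover. The crossover paragraph in protocol section 10 calls for separate listings and merely permits summary tables with at least 10 such patients. The SAP makes crossover safety summaries conditional on more than 10.
- **Why 150 days.** It is tempting to say that the 150-day window was set to catch delayed immune-related events. By the amendment rationales, that was one reason for the earlier extension to 90 days (Amendment 02). The move from 90 to 150 days rests on half-life and a safety margin (Amendment 03).
- **Other documents.** The SAP covers the final CSR only. It refers to an interim CSR and to separate output shells, and whether either contains this table cannot be seen.

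None of this supplies the omitted item or explains its absence. A shortened plan may drop a table that the protocol promised, but it should say so.

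**Conclusion.** The point holds as an undeclared departure of the SAP from the protocol, limited to one summary. SAP 2.8.1 omits the combined-period summary of related AESIs, so no grouped count of related AESIs covers 120 of the 150 days (80%) after the last PDR001 dose.

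The 80% is a share of calendar days after the last dose for a patient followed the full 150 days. A reader might take it as the share of AESIs missed. The documents give no event rates to support that, and the on-treatment table covers the whole dosing period as well as the first 30 days after it.

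The conclusion assumes that the SAP's two-item list is complete as written and that the output shells do not add the table. No efficacy result and no data collection is affected.

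**What to change.** In SAP 2.8.1, add a third item, AESIs related to study treatment, to the list of PDR001 summaries for events that begin or worsen in either the on-treatment or the post-treatment period. Use the AESI groupings already defined there and report the number and percentage of patients with at least one such event per grouping. If the sponsor prefers not to produce it, record the omission and the reason in SAP section 4.

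A crossover column may be added under the SAP's existing more-than-10-patients condition. That is an optional improvement, and protocol 10.5.3.2 does not require it.

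While editing, reconcile the wording in SAP 2.8 that treats the end of safety follow-up as 30 days after the last PDR001 dose, since the protocol's safety follow-up runs to 150 days.

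Cost: one extra table. The data, the groupings and the combined-period rule are already specified.
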